Following the completion of the treatment period, patients will be followed up for an additional 24 weeks (for patients healed and non-healed [and not meeting discontinuation criteria] at Week 8) and will be evaluated at the end of the follow-up period. At the investigator's discretion, the subject may be seen for an Unscheduled Visit to evaluate for safety. Patients who prematurely discontinue for whatever reason will not be followed post discontinuation and should have Visit 6 assessments completed.

At Visit 1, eligible patients will be instructed to discontinue all topical ophthalmic medications and will only be allowed to use commercially available preservative-free artificial tears provided by the sponsor to be used up to four times per day during the screening period. At the conclusion of the Baseline Visit (Visit 2) eligible patients will be dispensed a 2-week supply of Study Product from the onsite freezer in a sealed bag and will be instructed to self-administer the Study Product one drop six times a day starting on the day after Day 0/ Visit 2 through Week 8 of the controlled treatment period.

A two week supply of study product will additionally be dispensed to the patients during the treatment period at Visits 3, 4 and 5/Weeks 2, 4 and 6.

Starting from Visit 2, only the study product will be allowed. Preservative free AT provided by the sponsor *will not* be used during the study product treatment period. After the 8 weeks of study product treatment, and during the follow up period, AT should be used only if strictly needed. The use of AT will be tracked in the daily dosing diary.

At Visit 6 (End of Treatment), patients will be assessed for corneal healing.

Rescue Therapy: Commercially available preservative free artificial tears (AT) provided by Sponsor are not allowed during the treatment period. Per the investigators discretion if the patient requires rescue therapy during the 8-week treatment period then they can receive artificial tears provided by the sponsor up to four times per day. The frequency of rescue therapy must be documented in the patient's diary.

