6.2. EARLY WITHDRAWAL FROM STUDY

A premature discontinuation will occur when a patient who signed the ICF ceases participation in the study, regardless of circumstances, before the completion of the study protocol procedures. Patients can be prematurely discontinued from the study for one of the following reasons:

- Progression from Stage 1 to Stage 2 or Stage 3 NK, or corneal melting/perforation
- At the PI discretion patient is considered to be a non-responder (no improvement from baseline).
- In the qualifying/Study Eye, the FCS is unchanged (Grade=3) from baseline after 8 weeks of treatment in the qualifying NEI zone or there is an increase in FCS ≥1 within a non-qualifying NEI zone in the same eye.
- Decrease in BCDVA by >10 ETDRS letters
- Onset of infection (bacterial or viral)
- Protocol violation, including lack of compliance defined as <80% of doses taken based on diary documentation between treatment clinic visits.
- Withdrawal of consent
- Lost to follow-up during the treatment period (Every effort must be made to contact the patient; a registered letter must be sent)
- Study terminated by the Sponsor
- Other reasons, such as administrative reasons or pregnancy
- Development of AE or unacceptable toxicity per the investigator's discretion, precluding further therapy with the study drug.
- Severe protocol violations, such as an incorrect treatment administration, or a concomitant use of not permitted medications. Before removal, these cases should first be discussed with Dompé.

The reasons for premature discontinuation from the study will be reflected on the Study Termination Record of the CRF. For patients who prematurely discontinue, Visit 6 procedures will be completed, and these patients will be considered off study and will no longer be followed.

For patients that discontinue prematurely, the investigator should refer patients for further treatment as appropriate.

Replacement Procedures

Patients in this study who prematurely discontinue before completion of 8 weeks of treatment with OxervateTM will be replaced. Patients prematurely discontinuing during follow up treatment will not be replaced.

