7.1.3. Safety endpoints

1. Adverse Events (AEs) and Treatment-emergent adverse events (TEAEs), assessed throughout the study

EVALUATION OF ADVERSE EVENTS AND SAFETY INFORMATION

8.1. **DEFINITIONS**

Adverse Event

An **Adverse Event** (**AE**) is defined as any untoward medical occurrence in a patient or clinical investigation subject administered a pharmaceutical product and which does not necessarily have a causal relationship with this treatment. An AE can therefore be any unfavorable and unintended sign (including an abnormal laboratory finding), symptom, or disease temporally associated with the use of a pharmaceutical product, whether or not considered related to the Study Product.

This definition includes an exacerbation of preexisting medical conditions or events, historical conditions not present prior to study treatment, which reappear following study treatment, intercurrent illnesses, hypersensitivity reactions, drug-drug or drug-food interactions, medication errors, overdose (both intentional or unintentional), drug misuse/abuse, false positive laboratory test, or the significant worsening of the disease under investigation.

Adverse Drug Reaction

An **Adverse Drug Reaction (ADR)** is defined as an adverse experience which is reasonably likely to have been caused by the drug. An adverse reaction, in contrast to an adverse event, is characterized by the fact that a causal relationship between a pharmaceutical product and an occurrence is suspected. Medical judgment should be used to determine the relationship, considering all relevant factors, including pattern of reaction, temporal relationship, de-challenge or re-challenge, confounding factors such as concomitant medication, concomitant diseases, and relevant history.

Adverse drug reactions may arise from use of the Study Product within or outside the terms of the marketing authorization or from occupational exposure. Conditions of use outside the marketing authorization include off-label use, overdose, misuse, abuse, and medication errors, occupational exposure.

The Investigator carefully assesses relationship between event and Study drug using the information below

Arguments that may suggest a reasonable causal relationship could be:

- The event is consistent with the known pharmacology of the drug
- The event is known to be caused by or attributed to the drug
- A plausible time to onset of the event relative to the time of drug exposure

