8.3. RECORDING

AEs will be collected and recorded for any untoward event that occurs in a patient from the time he or she signs the ICF for the trial until 24 weeks after the last dose of Study Product. Thus, any untoward medical occurrences or unfavorable and unintended signs, symptoms, or diseases that occur in the pretreatment, treatment, or post treatment period are to be considered AEs and/or SAEs, and consequently recorded and reported as such. Should a non-serious AE become serious, the Investigator will then follow the same reporting procedures as for SAEs.

Each AE will be described by:

- Its duration (start and stop dates)
- Severity
- Its relationship to the study drug; (suspected/unsuspected)
- Action(s) taken
- Outcome

Medical conditions/diseases, or cancer related signs/symptoms present before starting study treatment shall be documented in the medical history section of the CRF; these conditions are considered AEs only if they increase either in frequency or severity once informed consent has been signed.

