8.6. ADVERSE EVENTS CAUSING TREATMENT DISCONTINUATION

If a patient is withdrawn from the study as a consequence of an AE, this must be recorded and reasoned in the CRF, and the patient must be followed up until the resolution of the AE or as instructed by the medical monitor.

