1.3.4 Safety Assessments

1.3.4.1 Adverse events

Adverse events (AEs) will be collected and recorded for any untoward event that occurs in a patient from the time he or she signs the ICF for the trial until 24 weeks after the last dose of Study Product. Thus, any untoward medical occurrences or unfavorable and unintended signs, symptoms, or diseases that occur in the pretreatment, treatment, or post treatment period are to be considered AEs and/or SAEs, and consequently recorded and reported as such. Should a non-serious AE become serious, the Investigator will then follow the same reporting procedures as for SAEs. Each AE will be recorded for duration

Confidential

Final Version 1.0, 2021-05-20

(start and stop dates), severity, relationship to the study drug, action(s) taken, outcome.

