6.1 Adverse Events

Adverse events data is collected from the time that informed consent was given, for the duration of the trial on the 'Adverse Events' eCRF page. All events in the clinical database regardless of when they occurred will be provided in data listings. Adverse events will be classified according to the MedDRA to the levels of SOC and PT. SOC will be sorted alphabetically and PT within each SOC will be sorted by overall descending order of frequency.

Pre-treatment AEs are defined as AEs that started during the pre-treatment period (date of informed consent up to the time before the first administration of the study product. Pre-treatment AEs, if any, will be listed only.

Treatment-emergent adverse events (TEAEs) are those with onset after the first dose of study product. Only treatment-emergent events will be summarized.

An overall summary will be presented which gives the number and percentage of subjects that experienced any TEAE, experienced any treatment related TEAE, permanently discontinued treatment due to a TEAE, interrupted treatment due to a TEAE, experienced a serious AE (SAE), and AEs leading to death.

The number and percentage of subjects experiencing one or more events will be tabulated by SOC and PT. In addition, similar tables by SOC and PT will be displayed further by maximum severity, and by closest relationship to treatment. For summary, the TEAEs with relationship to treatment reported as "None" or "Unlikely" are considered "Not Related", and "Possible", "Probable", or "Highly Probable" are considered "Related".

Summary tables will be prepared also for the number and percentage of subjects experiencing one or more events classified as: On Treatment Period (AEs started between the day of first administration of the study product and the day of last administration of the study product), and On Follow-up Period (AEs started after the day of last administration of the study product).

In summary tables for ocular adverse events, AEs occurring in both eyes will be summarized once at the greater severity or closer relationship to study drug.

The number of and percentage of subjects experiencing AEs leading to premature discontinuation from the study will be tabulated and listed.

Confidential Final Version 1.0, 2021-05-20

A listing of serious TEAEs will be also provided.

A glossary listing that shows the verbatim terms assigned to each SOC and PT will be provided.

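### Protocol and SAP each end follow-up at discontinuation yet collect AEs to 24 weeks past the last dose, and follow-up AE percentages default to the FAS

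*Protocol*

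**What the plan says.** **Follow-up after discontinuation.** The Protocol synopsis states: "Patients who prematurely discontinue for whatever reason will not be followed post discontinuation and should have Visit 6 assessments completed". Protocol 3.3 and SAP 1.2 use the same sentence. Protocol 6.2 adds that, after the Visit 6 procedures, "these patients will be considered off study and will no longer be followed".

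**AE collection window.** Protocol 8.3 records AEs from when the patient "signs the ICF for the trial until 24 weeks after the last dose of Study Product". SAP 1.3.4.1 has the same end point: "until 24 weeks after the last dose of Study Product". Neither makes an exception for discontinued patients. Two looser wordings also appear. Protocol 7.1.3 has AEs "assessed throughout the study", and SAP 6.1 says "Adverse events data is collected from the time that informed consent was given, for the duration of the trial".

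**Limited follow-up after leaving.**
- Protocol 8.6, for withdrawal because of an AE: "the patient must be followed up until the resolution of the AE or as instructed by the medical monitor".
- Protocol 8.3.1 has AEs followed until they resolve or stabilise.
- Protocol 8.4.1 has SAEs reported after participation ends if the investigator learns of them. Protocol 8.1 treats AESIs in the same way as SAEs.

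**Analysis.** SAP 6.1 plans the number and percentage of subjects with AEs in two periods. One is "On Follow-up Period (AEs started after the day of last administration of the study product". It names no population for that period. SAP 2.6.3 and SAP 6 put safety summaries on the FAS, meaning enrolled patients with at least one dose.

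**The concern.** A site cannot satisfy both instructions for a discontinued patient. If follow-up stops at the Visit 6 procedures, AEs are not being collected to 24 weeks past the last dose, and a report that repeats the 24-week window would describe something that was not done.

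The analysis inherits the problem. A patient who leaves at or before Week 8 remains in the FAS denominator for the follow-up period but has little or no chance of contributing an event to the numerator. The loss is also selective. The reasons for discontinuation in Protocol 3.3 and 6.2 include unchanged staining, progression, infection and loss of acuity.

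Safety is part of the primary objective (Protocol 3.1), and AEs are the only safety endpoint listed (Protocol 7.1.3). The descriptive percentages are the safety result of this study. On-treatment percentages are not affected by the denominator question.

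**Working it through.** The plan gives no AE rate or discontinuation rate, so it has no figure of its own to reproduce here. The first two steps compare passages; the third is arithmetic on assumed counts.

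**1. The passages side by side**

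| Statement | Protocol | SAP |
|---|---|---|
| No follow-up after discontinuation, whatever the reason | Synopsis, 3.3, 6.2 | 1.2 |
| AEs to 24 weeks past the last dose | 8.3 | 1.3.4.1 |
| AEs over the study or trial | 7.1.3 | 6.1 |

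The first two rows conflict within each column. The third row fits either reading and settles nothing.

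**2. What would be found in a discontinued patient**

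- Active AE questioning takes place at visits (Protocol 8.2). No visit is scheduled once the Visit 6 procedures are done.
- An AE already present is followed (Protocol 8.3.1, 8.6).
- A new SAE or AESI is reported only if the investigator hears of it (Protocol 8.4.1, 8.1).
- For a new non-serious AE, no route is given.

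Planned follow-up is Day 224 − Day 56 = 168 days = 24 weeks. A patient discontinued at Week 8 normally has close to none of it, because Protocol 6.1.5 asks for the sixth dose of the day to be taken before the Visit 6 evaluation. A patient who stops earlier has truncated observation, not necessarily none, because the Visit 6 procedures include an AE check (Protocol 6.1.6).

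**3. Effect of the denominator**

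Let N be the FAS size and E the number of patients who enter follow-up. Let x be those among E with a follow-up-period AE, and y those outside E with an AE starting after the last dose.

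- FAS percentage = (x + y)/N
- Percentage of those entering follow-up = x/E
- If y = 0, the first divided by the second is E/N.

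N = 35 requires that nobody stops early. The planned 35 are completers (Protocol 9.1), and patients who stop before 8 weeks are replaced (Protocol 6.2), so each early stopper raises the FAS above 35.

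Assumed counts, no early stoppers, x = 3, y = 0:

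| Leave at Week 8 | E | FAS percentage | Percentage of those entering |
|---|---|---|---|
| 0 | 35 | 3/35 = 8.6% | 3/35 = 8.6% |
| 5 | 30 | 3/35 = 8.6% | 3/30 = 10.0% |

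In the second row the gap is 1.4 points. The ratio is 30/35 = 0.857, so the FAS figure is 14.3% lower in relative terms. The exact 95% intervals are 1.8–23.1% for 3/35 and 2.1–26.5% for 3/30, which overlap widely.

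**4. Can the FAS figure be the higher one?** Yes, whenever y/(N − E) exceeds x/E. Assume 35 completers all enter follow-up, 3 of them with an AE, and 2 early stoppers, 1 of whom has an AE after the last dose that is found at the Visit 6 check. The FAS percentage is 4/37 = 10.8%, against 3/35 = 8.6% of those entering.

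**The case against.** **The denominator is stated.** SAP 2.6.3 and 6 name the FAS for safety, and using one safety population throughout a single-arm descriptive study is a legitimate choice. This stands: the issue is the choice of denominator, not a missing definition. However, the SAP does narrow the set for other follow-up results. Remaining healed is reported on Week 8 healers and on the FTS (SAP 5.2), and Appendix 2 lists follow-up artificial-tear exposure on the FTS.

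**Protocol 6.2 may be meant as the specific rule that limits 8.3.** That is possible, but no passage says so.

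**Much can be recovered.** All AEs are listed whenever they occurred, and AEs leading to discontinuation are tabulated (SAP 6.1). Disposition and visit completion are also tabulated (SAP 3.1, 3.2). Significant worsening of the disease is itself an AE (Protocol 8.1), so an event that triggers discontinuation should be captured when it happens. This stands and keeps the point minor. It does not supply new non-serious AEs that nobody asked about.

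**Stronger readings that the documents do not support.**
- A reader might infer that the Protocol and the SAP disagree with each other. They do not: each carries both statements in near-identical words.
- A reader might infer that the FAS percentage can only be too low. Against the percentage of those entering follow-up, the 4/37 example shows that it can be higher.
- A reader might infer from the Appendix 2 list, which has no title for AEs by period, that the analysis was dropped. The list has no period-specific title for concomitant medications either, although SAP 4.2 splits them by period. The mock shells are a separate document (SAP 1), so the missing title shows little.

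**Conclusion.** The concern holds, as a minor point, in two parts.

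First, both documents contain incompatible statements about AE collection after discontinuation, and the provisions for existing AEs and for SAEs do not close the gap for new non-serious events. This part rests on the text alone.

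Second, applying the FAS rule to follow-up-period percentages counts patients who left at or before Week 8 as event-free when they were barely or not observed. Compared with the incidence that full follow-up would show, the percentage tends to be too low. The size is unknown, and zero if nobody discontinues. The 8.6% against 10.0% example assumes 3 affected patients, 5 discontinued at Week 8 and no early stoppers; it illustrates and does not estimate.

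A reader might try to derive a size from the planned 72% healing rate, which leaves 35 × 0.28 = 9.8 patients unhealed. That does not work. Unhealed Grade 2 patients who meet no discontinuation criterion continue, the share still at Grade 3 is not given, and the other discontinuation criteria are not quantified.

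No hypothesis test is affected. No change of denominator recovers events that were never observed.

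**What to change.** (a) Reconcile the Protocol synopsis, 3.3, 6.2, 8.3 and 8.6 with SAP 1.2, 1.3.4.1 and 6.1, so that the stated AE window matches what is collected for discontinued patients. Which follow-up rule to adopt is a clinical matter for the sponsor, and none is proposed here.

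(b) In SAP 6.1, for AEs in the follow-up period:
- give the percentage with the number of FAS patients who entered follow-up after Visit 6 as the denominator, alongside the FAS percentage;
- list separately any AEs starting after the last dose in patients who did not enter follow-up, so that an early stopper's event is not lost from view;
- give the median and range of days observed after the last dose, against the 168 planned, since patients discontinued during follow-up are truncated too.

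The cost is a clarifying sentence where the passages conflict, revised SAP 6.1 wording and minor programming. The follow-up percentage may look slightly less favourable.

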6.3. END OF STUDY

For this trial, the End of Study is defined as the date of the last visit of the last subject.

7. ENDPOINTS

7.1. STUDY ENDPOINTS

7.1.1. Efficacy endpoints

- 1. Percentage of patients who experience epithelial healing at 4 and 8 weeks. (Epithelial healing is defined as Grade 1 or absence of staining (Grade 0) in a previously qualifying zone.)
- 2. Percentage of patients who remain healed (as defined in #1 above) throughout the follow-up period.
- 3. Schirmer I change from baseline to weeks 4 & 8
- **4.** TFBUT change from baseline to weeks 4 & 8
- 5. Percentage of patients that achieve an improvement in corneal sensitivity in the NEI zone used to qualify in the study eye as measured by the Cochet-Bonnet aesthesiometer at 4 and 8 weeks, and at the last visit (week 32).
- **6.** Quality of life questionnaires change from baseline at week 8 and week 32
- 7. IDEEL
- **8.** EQ-5D-5L
- **9.** Mean change in BCDVA from baseline to Week 8.
- **10.** Percentage of patients that achieve a 15- letter gain in BCDVA at 4 and 8 weeks.

7.1.2. Exploratory Efficacy Endpoints

1. Frequency of preservative free artificial tears use (n° drops/day) during the follow up period.

At selected sites:

The following may be evaluated as part of a post-hoc analysis:

- **2.** Change from baseline structural nerve regeneration (density, length, nerve density, tortuosity) per confocal microscopy.
- **3.** Change from baseline in epithelial thickness per anterior segment OCT.

7.1.3. Safety endpoints

1. Adverse Events (AEs) and Treatment-emergent adverse events (TEAEs), assessed throughout the study

EVALUATION OF ADVERSE EVENTS AND SAFETY INFORMATION

8.1. **DEFINITIONS**

Adverse Event

An **Adverse Event** (**AE**) is defined as any untoward medical occurrence in a patient or clinical investigation subject administered a pharmaceutical product and which does not necessarily have a causal relationship with this treatment. An AE can therefore be any unfavorable and unintended sign (including an abnormal laboratory finding), symptom, or disease temporally associated with the use of a pharmaceutical product, whether or not considered related to the Study Product.

This definition includes an exacerbation of preexisting medical conditions or events, historical conditions not present prior to study treatment, which reappear following study treatment, intercurrent illnesses, hypersensitivity reactions, drug-drug or drug-food interactions, medication errors, overdose (both intentional or unintentional), drug misuse/abuse, false positive laboratory test, or the significant worsening of the disease under investigation.

Adverse Drug Reaction

An **Adverse Drug Reaction (ADR)** is defined as an adverse experience which is reasonably likely to have been caused by the drug. An adverse reaction, in contrast to an adverse event, is characterized by the fact that a causal relationship between a pharmaceutical product and an occurrence is suspected. Medical judgment should be used to determine the relationship, considering all relevant factors, including pattern of reaction, temporal relationship, de-challenge or re-challenge, confounding factors such as concomitant medication, concomitant diseases, and relevant history.

Adverse drug reactions may arise from use of the Study Product within or outside the terms of the marketing authorization or from occupational exposure. Conditions of use outside the marketing authorization include off-label use, overdose, misuse, abuse, and medication errors, occupational exposure.

The Investigator carefully assesses relationship between event and Study drug using the information below

Arguments that may suggest a reasonable causal relationship could be:

- The event is consistent with the known pharmacology of the drug
- The event is known to be caused by or attributed to the drug
- A plausible time to onset of the event relative to the time of drug exposure
- Evidence that the event is reproducible when the drug is re-introduced
- No medically sound alternative etiologies that could explain the event (e.g. pre-existing or concomitant diseases, or co-medications)
- The event is typically drug-related and infrequent in the general population not exposed to the drug
- An indication of dose-response (i.e. greater effect size if the dose is increased, smaller effect size if dose is diminished)

Arguments that may suggest that there is no reasonable possibility of a causal relationship could be:

- No plausible time to onset of the event relative to the time of drug exposure is evident (e.g. pretreatment cases, diagnosis of cancer or chronic disease within days/weeks of drug administration; an allergic reaction weeks after discontinuation of the drug concerned)
- Continuation of the event despite the withdrawal of the medication, considering the pharmacological properties of the compound (e.g. after 5 half-lives). Of note, this criterion may not be applicable to events whose time course is prolonged despite removing the original trigger.
- Additional arguments amongst those stated before, like alternative explanation (e.g. situations where other drugs or underlying diseases appear to provide a more likely explanation for the observed event than the drug concerned)
- Disappearance of the event even though the study drug treatment continues or remains unchanged.

Adverse events are to be considered unrelated if the relationship to the study drug as described in the table in section [8.3.2] is none or unlikely; whereas any AE reported in the study having a possible, probable or highly probable relationship to study drug will be considered as an ADR. [For the purposes of safety reporting, "reasonable possibility" means there are facts (evidence) or arguments to suggest a causal relationship between the drug and the adverse event.]

Adverse Event of Special Interest (AESI)

The term AESI relates to any specific AE that has been identified at the project level as being of particular concern for prospective safety monitoring and safety assessment within the study, e.g. the potential for AEs based on knowledge from other compounds in the same class.

In the present study, the following sight-threatening events will follow into the definition of AESI and will be considered equivalent to a SAE and will be reported following the procedures described below for the reporting of a SAE:

- Adverse Events that caused a decrease in visual acuity of >30 ETDRS letters or > +0.6 LogMAR (compared with the last assessment of visual acuity at the last visit) lasting >1 hour.
- Adverse Events that caused a decrease in visual acuity to the level of Light Perception or worse lasting >1 hour.
- Adverse Events that required surgical intervention (e.g., conventional surgery, vitreous tap or biopsy with intravitreal injection of anti-infectives, or laser or retinal cryopexy with gas) to prevent permanent loss of sight.
- Adverse Events associated with severe intraocular inflammation (i.e., 4+ anterior chamber cell/flare or 4+ vitritis).
- Adverse Events that, in the opinion of the investigator, required medical intervention to prevent permanent loss of sight.

Serious Adverse Event

A Serious Adverse Event (SAE) is defined as any untoward medical occurrence that at any dose:

- results in death,
- is life-threatening (i.e. the patient was at risk of death at the time of the event. It does not refer to an event which hypothetically might have caused death if it were more severe),
- requires inpatient hospitalization or prolongation of existing hospitalization,

NOTE: In general, hospitalization means that the individual remained at the hospital or emergency ward for observation and/or treatment (usually involving an overnight stay) that would not have been appropriate in the physician's office or an out-patient setting. Complications that occur during hospitalization are AEs. If a complication prolongs hospitalization or fulfills any other serious criteria, the event is serious. When in doubt as to whether "hospitalization" occurred, the event should be considered serious.

• results in persistent or significant disability/incapacity,

NOTE: This definition is not intended to include experiences of relatively minor medical significance such as uncomplicated headache, nausea, vomiting, diarrhea, influenza, or accidental trauma (e.g., sprained ankle) which may interfere or prevent everyday life functions, but do not constitute a substantial disruption.

- is a congenital anomaly/birth defect,
- is medically significant or important medical condition, i.e. an important medical event that based upon appropriate medical judgment, may jeopardize the patient, and may require medical or surgical intervention to prevent one of the outcomes listed above.

An important medical condition is an event that may not result in death, be life-threatening, or require hospitalization but may be considered a SAE when, based upon appropriate medical judgment, it may jeopardize the patient and may require medical or surgical intervention to prevent one of the outcomes listed above. Examples of such medical events include allergic bronchospasm requiring intensive treatment in an emergency room or at home, blood dyscrasias or convulsions that do not result in patient hospitalization, or the development of drug dependency or drug abuse.

Pre-planned hospitalization or hospitalization for routine treatment or monitoring of the studied indication, not associated with any deterioration in condition are not considered to be SAEs.

These events must be recorded in the AE page of the CRF where a variable will be ticked to indicate that they are not SAEs.

Death shall always be reported as SAE. Cause of death shall always be specified when known.

Any preplanned surgery or procedure should be clearly documented in the site source documents by the medically qualified Investigator at the time of the patient's entry into the study. If it has not been documented at the time of the patient's entry into the study, then it should be documented as a serious adverse event and reported to Dompé.

Dompé considers cancer and abortion (spontaneous or non-spontaneous) as serious adverse events, as well as any suspected transmission via a medicinal product of an infectious agent is considered a serious adverse reaction.

Unexpected Adverse Events

An AE or ADR is considered unexpected if it is not listed in the package insert. An event is unexpected also when it is not listed at the specificity or severity that has been observed and listed in the package insert.

The determination of expectedness shall be made based on the package insert. It is the responsibility of the Sponsor to assess whether an AE is expected or unexpected.

Suspected serious unexpected adverse reaction

A suspected serious unexpected adverse reaction (SUSAR) is defined as an adverse reaction that is both unexpected (not consistent with the applicable product information) and meets the definition of a Serious Adverse Reaction.

